**NCT05141435**

**DATE: August 1, 2022**

# **NHFOV vs nCPAP in Very Preterm Infants With Respiratory Distress Syndrome: A Multi-center, Prospective, Randomized, Controlled Clinical Superior Trial**

## **Trial Design**

This will be a multicentre, randomised controlled, superiority trial conducted in 20 tertiary NICUs in China from August 2022 to August 2024. We perform this trial to compare the need for invasive mechanical ventilation (IMV) in very preterm infants with respiratory distress syndrome (RDS) randomized to Noninvasive high-Frequency oscillatory ventilation (NHFOV) versus nasal continuous positive airway pressure (NCPAP).

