### **Randomization**

Neonates will be randomised and assigned either to NCPAP or NHFOV arms with a 1:1 ratio, when patients fulfil all inclusion criteria. Simple randomisation will be done according to a computer-generated random number table and will be posted in a

specific secured website available on 24/7. Twins will all be allocated in the same treatment group. Infants randomised to one arm cannot crossover to the other or vice-versa during the study.

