### **Sample size calculation**

According to the results of our last multicentre study, the risk of failure while receiving NCPAP for very preterm infants with RDS was 30%, and a reduction of 20% for babies receiving NHFOV. We decide to aim a difference of 15% in the rate of the respiratory support failure. Considering an alpha error of 0.05 and a power of 90%, 170 neonates would be needed in each group.

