### **Statistical methods**

Outcomes will be analysed on an intention-to-treat basis. We will calculate a risk difference (with 95%CI) for dichotomous outcomes and mean (with 95%CI) or median (25–75th percentile, using Hodges-Lehmann) differences for continuous outcomes between the study groups. Continuous variables will be compared using

Student's t test or the Mann-Whitney rank sum test as appropriate. Categorical variables were compared using the  $\chi^2$  test. P values  $< 0.05$  were considered statistically significant.

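### Centre enters neither the randomisation nor the primary analysis of this 20-unit trial; a random centre intercept would give a small precision gain at almost no cost

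*Combined protocol and SAP*

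**What the plan says.** The Trial Design section states that the study is "conducted in 20 tertiary NICUs in China". The Randomization section has infants "assigned either to NCPAP or NHFOV arms with a 1:1 ratio" and specifies that "Simple randomisation will be done according to a computer-generated random number table"; it mentions no stratification or blocking by centre.

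Under Statistical methods, "We will calculate a risk difference (with 95%CI) for dichotomous outcomes", and "Categorical variables were compared using the" chi-square test. No centre term, mixed model or other adjustment is mentioned. The Sample size calculation makes no allowance for centre.

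Two other sections leave room for units to differ. The fourth failure criterion under Primary outcomes is the treating physician's judgement that intubation is urgently needed. Other treatments or tests leaves some background care to local practice.

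**The concern.** If units differ in how readily they intubate, or in the risk of the infants they admit, failure rates will vary between centres. An analysis that ignores centre leaves this variation in the error of the risk difference. With 340/20 = 17 infants per centre on average, simple randomisation will leave some centres visibly unbalanced, and the unadjusted comparison makes no use of knowing which infant came from which unit.

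What is at stake is some width in the confidence interval and a little power. A model that uses centre can recover part of it from data already held.

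**Working it through.** **Inputs from the plan.** Control failure: "the risk of failure while receiving NCPAP for very preterm infants with RDS was 30" per cent. Target: "We decide to aim a difference of 15% in the rate of the respiratory support failure", read as 30% against 15%. Error rates: "Considering an alpha error of 0.05 and a power of 90" per cent; sidedness is not stated, so two-sided is assumed. Size: 170 per group, 340 in all, in 20 centres. **Not in the plan:** centre sizes and the between-centre variation. The latter is assumed to be a normal centre effect with SD 0 to 1.0 on the logit scale.

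**Step 1: reproduce the sample size.** With mean rate 0.225, n = [1.960·√(2·0.225·0.775) + 1.282·√(0.30·0.70 + 0.15·0.85)]² / 0.15² = (1.157 + 0.745)² / 0.0225 ≈ 161 per group. With the continuity correction, n = (161/4)·[1 + √(1 + 4/(161·0.15))]² ≈ 174. The stated 170 lies between the two, within 3% of 174.

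**Step 2: power of the planned test.** At 170 per group, z = (0.15·√170 − 1.960·0.5906)/0.5810 = 1.374, giving 91.5%.

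**Step 3: what adjustment can gain, by formula.** Take n = 17 per centre and intraclass correlation ρ (the share of outcome variance lying between centres). Under simple randomisation the information relative to the unadjusted analysis is:

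- random intercept: [1 − ρ/(1 + 16ρ)]/(1 − ρ)
- fixed centre effects: (16/17)/(1 − ρ)

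| ρ | Random intercept | Power | Fixed centres | Power |
|---|---|---|---|---|
| 0 | 1.000 | 91.5% | 0.941 | 89.9% |
| 0.05 | 1.023 | 92.1% | 0.991 | 91.3% |
| 0.10 | 1.068 | 93.1% | 1.046 | 92.6% |
| 0.15 | 1.125 | 94.2% | 1.107 | 93.9% |

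Fixed effects break even at ρ = 1/17 = 0.059. The random intercept loses nothing at ρ = 0.

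**Step 4: simulation at 30% against 15%.** Trials of 340 infants in 20 centres, simple randomisation, marginal rates held at the design values.

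| Centre SD (logit) | Centre sizes | Chi-square | Random intercept | Gain (points) |
|---|---|---|---|---|
| 0 | equal | 92.0% | 92.0% | 0 |
| 0 | unequal | 91.4% | 91.3% to 91.4% | −0.1 to 0 |
| 0.3 | unequal | 91.4% | 91.4% | 0 |
| 0.5 (ρ = 0.048) | equal | 91.9% | 92.1% | 0.2 |
| 0.6 | unequal | 91.1% to 92.0% | 92.0% to 92.9% | 0.5 to 1.1 |
| 0.75 (ρ = 0.099) | equal | 91.3% | 92.4% | 1.1 |
| 1.0 (ρ = 0.157) | equal | 91.1% | 93.6% | 2.5 |
| 1.0 | unequal | 91.3% to 91.6% | 93.6% to 94.1% | 2.3 to 2.6 |

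Ranges cover repeated simulations. With 6,000 runs the error of one power figure is √(0.915·0.085/6000) ≈ 0.4 points, so differences of a few tenths should not be read closely.

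**Step 5: type I error.** The unadjusted chi-square stayed at 4.7% to 5.3% for every SD tried. The random-intercept model with robust standard errors gave 5.3% at SD 0.6 and at SD 1.0. An uncorrected centre-clustered sandwich gave 7.4% to 8.3%, so the standard-error method has to be named.

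These calculations ignore the planned interim analyses and the allocation of twins to the same arm.

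**The case against.** The strongest reply is that nothing is broken. Under simple randomisation the chi-square is valid whether or not centres differ, and 170 per group delivers the stated 90% power. That stands in full.

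The size of the benefit also rests on a variation the documents do not give. The protocol standardises much of what might differ: numerical failure criteria, set ranges for both supports, one type of interface, and a common surfactant trigger and method. The physician-judgement criterion is a real source of centre differences, but of unknown size. An SD of 1.0 implies centre control failure rates of about 7% to 65% (5th to 95th percentile), so the lower gains are the safer expectation. This stands too, and is why the range starts at zero.

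A reader might infer more from the imbalance within centres. If every centre had 17 infants, a split of 12:5 or worse has probability 2·P(Bin(17, 0.5) ≤ 5) = 0.143, or 20 × 0.143 ≈ 2.9 centres. That is not bias: the imbalances are random in direction and already reflected in the chi-square's standard error. A reader might also infer that the randomisation should be stratified by centre. In small open-label units that makes allocation more predictable, so it is a trade-off, and the precision point does not need it.

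Finally, adjustment is not free in every form. A Mantel-Haenszel test stratified by centre costs 1.6 points when centres do not differ (91.6% against 90.0%). The claim of almost no cost holds only for the random intercept with a suitable standard error.

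**Conclusion.** The point holds as a small, optional improvement in precision. Centre is used nowhere in the design or analysis, and a random centre intercept would add roughly 0 to 2.5 power points at the design effect: nothing if centres are similar, 0.5 to 1 point at a logit SD of 0.6, and 2 to 2.5 points only if centres differ widely. Because it costs essentially nothing when centres do not differ, the choice does not depend on knowing the variation.

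The documents do not support reading this as an invalid test, an underpowered trial or a biased estimate. The figures assume normal centre effects on the logit scale, two-sided testing at 5%, and average centre sizes of 17 or an assumed unequal pattern.

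**What to change.** In Statistical methods, pre-specify before unblinding that the primary risk difference and its 95% CI come from a linear (identity-link) model for failure, with treatment as a fixed effect and centre as a random intercept, fitted by REML. State that standard errors are model-based or observation-level robust, and not an uncorrected centre-clustered sandwich. Keep the unadjusted risk difference and chi-square test as supportive.

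The cost is a few lines of text; each infant's centre is already known. The downside is a slightly more complex primary model, with no gain if centres barely differ. The randomisation stays as it is.

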### **Inclusion criteria:**

- i. GA between 240/7 and 286/7 weeks
- ii. Diagnosis of RDS. The diagnosis of RDS will be based on clinical manifestations (tachypnea, nasal flaring and or grunting) and a fraction of inspired oxygen (FiO2) greater than 0.25 for target saturation of peripheral oxygen (SpO2) 89%–94%
- iii. Age <2 hours
- iv. Informed parental consent has been obtained

### **Exclusion criteria**

- i. Intubated for any reasons at birth
- ii. major congenital malformations or known complex congenital heart disease
- iii. transferred out of the NICU before randomisation

### **Randomization**

Neonates will be randomised and assigned either to NCPAP or NHFOV arms with a 1:1 ratio, when patients fulfil all inclusion criteria. Simple randomisation will be done according to a computer-generated random number table and will be posted in a

specific secured website available on 24/7. Twins will all be allocated in the same treatment group. Infants randomised to one arm cannot crossover to the other or vice-versa during the study.

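### Twins are kept in one arm, but the tests, confidence intervals and sample size treat every infant as independent

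*Combined protocol and SAP*

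**What the plan says.** The allocation rule is under Randomization: "Twins will all be allocated in the same treatment group". The same section describes simple 1:1 randomisation of neonates and does not name the mother or pregnancy as the unit for multiple births. Exclusion criteria lists three reasons for exclusion, and multiple birth is not among them.

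The sample size is counted in infants. From a 30% failure rate on NCPAP, the section states "We decide to aim a difference of 15% in the rate of the respiratory support failure" and then "Considering an alpha error of 0.05 and a power of 90%, 170 neonates would be needed in each group". No design effect, twin share or within-pair correlation appears.

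Statistical methods plans risk differences with 95% confidence intervals for dichotomous outcomes, and Student's t or Mann-Whitney tests for continuous ones. For the rest, "Categorical variables were compared using the" chi-square test. The section names no generalised estimating equations (GEE), mixed model, cluster-robust variance or sensitivity analysis with one infant per pregnancy.

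**The concern.** For a twin pair, one randomisation decides the treatment of two infants. Every listed method assumes independent observations. Co-twins share a mother, antenatal exposures, a centre and essentially the same gestational age, so their need for invasive ventilation is likely to be positively correlated. Because pairs are never split between arms, that correlation adds to the variance of the treatment contrast, and an unadjusted analysis leaves it out.

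Two consequences follow, and they belong to different analyses. If the planned unadjusted tests are used, the type I error exceeds 5% and the interval for the primary risk difference is too narrow. If a valid clustered analysis is used instead, the error rate is right but 170 infants per arm carry less information than the power statement assumes. The secondary outcomes are affected in the same way.

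**Working it through.** **Inputs from the protocol.** Failure 30% on NCPAP against 15% on NHFOV (the 15-point difference); alpha 0.05, taken as two-sided because the section does not say; power 90%; 170 per arm; 1:1 allocation.

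**Inputs assumed.** The share f of infants enrolled as part of a complete pair, 0.20 to 0.40, and the within-pair correlation (ICC) of the outcome, 0.1 to 0.7. Neither is in the documents.

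**Step 1: reproduce the 170.** With mean rate 0.225, the usual two-proportion formula gives

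n = [1.96 × √(2 × 0.225 × 0.775) + 1.2816 × √(0.30 × 0.70 + 0.15 × 0.85)]² / 0.15² = (1.1575 + 0.7445)² / 0.0225 = 160.8, so 161 per arm.

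With a continuity correction the figure is 174. The stated 170 lies between them. It also equals 161 / 0.95 = 169.5 rounded up, although no dropout allowance is stated. All of these treat infants as independent.

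**Step 2: power at 170 with independent infants.** The standard error under the null is √(2 × 0.225 × 0.775 / 170) = 0.04529, and under the alternative √(0.3375 / 170) = 0.04456. Power = Φ[(0.15 − 1.96 × 0.04529) / 0.04456] = Φ(1.374) = 91.5%.

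**Step 3: design effect.** Each infant in a complete pair adds one covariance term with its co-twin, and a singleton adds none. For clusters of one or two, DE = 1 + f × ICC.

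**Step 4: consequences.**
- True type I error of the unadjusted test: 2 × [1 − Φ(1.96 / √DE)].
- Power of a valid analysis: the Step 2 formula with 170 / DE per arm.
- Power of the unadjusted test: only the standard error under the alternative is multiplied by √DE; the critical value is left as it is.
- Share by which the unadjusted standard error is too small: 1 − 1/√DE.
- Infants per arm for 90% valid power: 161 × DE, rounded up.

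For example, f = 0.30 and ICC = 0.5 give DE = 1.15. Type I error is 2 × [1 − Φ(1.828)] = 6.8%. The effective sample is 170 / 1.15 = 147.8 per arm, and valid power is 87.4%.

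| f | ICC | DE | SE too small by | Type I error, unadjusted | Power, unadjusted | Power, valid | Per arm for 90% |
|---|---|---|---|---|---|---|---|
| 0.20 | 0.1 | 1.02 | 1.0% | 5.2% | 91.3% | 91.0% | 165 |
| 0.20 | 0.3 | 1.06 | 2.9% | 5.7% | 90.9% | 89.9% | 171 |
| 0.30 | 0.3 | 1.09 | 4.2% | 6.1% | 90.6% | 89.1% | 176 |
| 0.30 | 0.5 | 1.15 | 6.7% | 6.8% | 90.0% | 87.4% | 186 |
| 0.40 | 0.7 | 1.28 | 11.6% | 8.3% | 88.8% | 83.7% | 207 |

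A simulation with 40,000 runs per scenario gave type I errors of 5.2% to 8.5% over the same range.

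**Step 5: break-even.** Valid power at 170 per arm equals 90% when DE = 1.057, that is f × ICC = 0.057. This corresponds to an ICC of about 0.29 at f = 0.20, 0.19 at f = 0.30 and 0.14 at f = 0.40.

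**Step 6: the interval.** At the planned rates the unadjusted half-width is 1.96 × 0.04456 = 8.7 percentage points. Multiplied by √DE, the correct half-width is 9.0 points at DE 1.06, 9.4 at 1.15 and 9.9 at 1.28.

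**The case against.** The case against disputes the size of the problem rather than its existence.

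- **The size is undocumented.** The standard errors are too small only if co-twins' outcomes are positively correlated and enough complete pairs enrol. The documents give neither figure. This stands: the omission is certain, the amount is not.
- **Co-enrolment is narrower than the twin rate.** A pair counts only if both infants have RDS with the required oxygen need, are under 2 hours old, have consent and were not intubated at birth. A share of 20% to 40% may be high. This also stands, and the documents cannot settle it. At f = 0.10 and ICC = 0.3 the design effect is 1.03, type I error 5.4% and valid power 90.7%.
- **The plan has some slack.** Since 170 exceeds the uncorrected 161, a design effect of up to about 1.057 is absorbed. This is true for power, but the slack does nothing for type I error or interval width, because those depend on the analysis and not on the number of infants.
- **Power is a secondary matter.** Under the planned tests it stays near 89% to 91%. This is right, but that power is held up by the inflated error rate.
- **A missing birth identifier is not shown.** Data collection refers to baseline clinical information only in general terms, so the field may exist. The remedy is to confirm it.

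None of these points supplies a provision for pairing, and no other section does.

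**Conclusion.** The concern holds. The plan creates clusters through its allocation rule and then sizes and analyses the trial as though there were none. Under any positive co-twin correlation the error goes one way: intervals too narrow and P values too small, which favours a false finding of superiority.

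The size is modest and conditional. Over the assumed ranges, the unadjusted standard error is about 1% to 12% too small, the true type I error is 5.2% to 8.3%, and valid power at 170 per arm runs from 91.0% down to 83.7%. The worst figures need both assumed inputs at their upper ends. The stated 90% may or may not survive; it does so only while f × ICC is at most about 0.057.

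These figures refer to a single final test with 170 infants analysed per arm. They leave out any loss of infants and the three interim analyses planned under Data monitoring board. The change should be made, but the point does not undermine the design.

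**What to change.** 1. **Randomization.** Name the mother or pregnancy as the unit for multiple births, and say how triplets and larger sets are handled.
2. **Statistical methods.** Keep the risk difference as the primary measure, but compute its interval and P value with standard errors clustered on the mother, or by GEE with a binomial outcome and identity link. The robust standard error is a sensible fallback if the identity link does not converge. Cluster numbers are ample: even with 40% of 340 infants in pairs there would be 68 pairs and 204 singletons, or 272 clusters. For continuous outcomes, use a linear model with clustered standard errors for mean differences and a bootstrap that resamples mothers for Hodges-Lehmann differences. An analysis with one randomly chosen infant per pregnancy would be a useful sensitivity check.
3. **Data collection.** Confirm that the case report form holds a mother or birth identifier, and add one if not.
4. **Sample size calculation.** Say that 90% is the power before clustering, and give the power under a stated twin share and ICC with the formula above.

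The cost is plan wording and at most one data field, with no extra infants required. The interval widens by a factor of √DE, about 3% at DE 1.06 and 13% at DE 1.28, and the stated power may fall slightly. If the sponsor wants to hold 90% power instead, the table in the working gives the number per arm. The choice should be fixed before any outcome data are seen.

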### **Blinding**

Operators and care providers will not be blinded, and the outcome assessors and data analysts will be blinded to the intervention

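### When twins qualify at different times, the later twin's arm is already known while its eligibility is still being judged

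*Combined protocol and SAP*

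**What the plan says.** The Randomization section sets the unit and the moment of entry: "Neonates will be randomised and assigned either to NCPAP or NHFOV arms with a 1:1 ratio, when patients fulfil all inclusion criteria". The sequence is simple randomisation through a secured website. The same section then adds the twin rule: "Twins will all be allocated in the same treatment group". It does not say whether a pair is registered together or one infant at a time.

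Other sections bear on the point:

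- **Blinding:** "Operators and care providers will not be blinded, and the outcome assessors and data analysts will be blinded to the intervention".
- **Inclusion criteria:** "The diagnosis of RDS will be based on clinical manifestations (tachypnea, nasal flaring and or grunting) and a fraction of inspired oxygen" above 0.25 at a stated saturation target. Age must be under 2 hours and parental consent is required.
- **Exclusion criteria:** infants intubated at birth are excluded.
- **Ethics and dissemination:** consent may be obtained before birth or on NICU admission.
- **Data collection:** eligibility information, baseline clinical data, the Silverman score and the CRIB-II score are recorded before the intervention.

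**The concern.** Allocation concealment means that whoever decides on entry cannot know the arm the infant would join. For a singleton or a first twin the website provides this. For a co-twin who qualifies later, the same-arm rule has already fixed the arm.

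Suppose, hypothetically, that one twin needs FiO2 0.30 at 30 minutes and is randomised, while the other needs 0.23 and passes 0.25 only at 80 minutes. The second infant is still within the 2-hour window, and its arm can be seen at the bedside. Its eligibility rests on signs that are judged and on an oxygen setting that staff titrate.

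If knowledge of the arm influences whether such infants are entered, the arms can differ at baseline. Intention-to-treat does not repair this, because an infant who is never entered is not in the analysis set. Blinded outcome assessment does not repair it either. The within-pair correlation of twins is a separate matter, and a clustered analysis would not correct selection at entry.

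**Working it through.** **1. The passages side by side.** Entry is per infant and depends on when that infant meets the criteria. Twins must share an arm. Together these imply that, when twins qualify at different times, the second infant's arm is set before the second infant is entered. Staff are unblinded, so the arm is known. No section requires joint assessment, joint registration, or an eligibility judgement by someone unaware of the first twin's arm.

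**2. The plan's own figure.** The Sample size calculation section gives 30% failure on NCPAP, a 15% difference (read here as percentage points, 30% against 15%), alpha 0.05 (taken as two-sided), power 90%, and 170 per group.

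- Pooled two-proportion formula: n = [1.960 × √(2 × 0.225 × 0.775) + 1.2816 × √(0.30 × 0.70 + 0.15 × 0.85)]² / 0.15² ≈ 161 per group.
- With continuity correction: 174 per group.
- Power at 170 per group, without correction: 91.5%.

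The stated 170 is close to the corrected figure. This point does not change it.

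**3. Size of a possible shift.** The documents give neither the twin share nor any rate of non-entry, so the following are assumptions:

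- twin share of infants 20–40%, so the second-twin share is s = twin share / 2 = 10–20%;
- L = 10–30% of second twins not entered, in one arm only;
- true failure rate 30% (the plan's control figure);
- failure risk r among the omitted infants.

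Arm failure rate after omission = (0.30 − s × L × r) / (1 − s × L).

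| Twin share | s | L | r | Arm failure rate | Shift (points) |
|---|---|---|---|---|---|
| 20% | 0.10 | 10% | 0.60 | (0.30 − 0.006)/0.99 = 29.7% | −0.3 |
| 30% | 0.15 | 30% | 0.60 | (0.30 − 0.027)/0.955 = 28.6% | −1.4 |
| 40% | 0.20 | 30% | 0.60 | (0.30 − 0.036)/0.94 = 28.1% | −1.9 |
| 40% | 0.20 | 30% | 0.15 | (0.30 − 0.009)/0.94 = 31.0% | +1.0 |

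The first three rows assume that the omitted twins are sicker, at double the average risk. The last assumes that they are milder, at half the average risk. The sign reverses.

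**4. If many pairs qualify together.** Only later-qualifying co-twins are exposed. If half the pairs qualify together, s is halved. With r = 0.60 the largest shift is (0.30 − 0.018)/0.97 = 29.1%, or −0.9 points. The smallest is (0.30 − 0.003)/0.995 = 29.8%, or −0.15 points.

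**5. A second model as a check.** Assume no true effect, 170 per group, and that a fraction of the second twins who would have failed are not entered in one arm. Over the same 20–40% twin share, a fraction of 10–30% gives a spurious difference of 0.2 to 1.3 points and a two-sided type I error of 5.0% to 5.8%. An extreme fraction of 50% at a 40% twin share gives 2.2 points and 7.2%.

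**The case against.** The strongest reply is that the plan never describes sequential entry of twins. The same-arm sentence is compatible with registering a pair together under one allocation, in which case the problem does not arise. This stands in part: sequential entry is an inference. But entry is tied to when the individual infant qualifies, and nothing requires the pair to be handled jointly. A site that follows the text as written will lose concealment whenever twins qualify at different times.

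Several routes to selection are weak, and this also stands:

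- Twins share parents, so consent for the first often settles consent for both, and consent before birth precedes any allocation.
- Intubating the second twin after the first has been randomised in the NICU does not meet the exclusion, which covers intubation at birth only.
- The oxygen criterion is a number set against a stated target, although the setting is titrated at the bedside and the clinical signs are judged. The plan does not name who decides eligibility. Bedside staff is the natural reading.

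A reader might infer that the trial as a whole lacks allocation concealment. The documents do not support that, because the website conceals the arm for singletons and first twins. A reader might also infer a systematic and undetectable bias. The direction is not fixed: if severity drives timing, the later twin tends to be the milder one. The selection is also partly checkable, because eligibility data and CRIB-II scores are collected before the intervention. What the plan lacks is a stated record of co-twins who were screened and not entered.

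**Conclusion.** The gap is real and limited. Under the stated rules, allocation is not concealed for a co-twin who qualifies after its sibling's arm is known. Under the assumed ranges the effect on one arm's failure rate is at most about 2 percentage points against a 15-point target. It can go in either direction, and it shrinks as more pairs qualify together. All of these sizes rest on an assumed twin share and an assumed rate of selective non-entry. This is a risk in the procedure, not evidence that selection occurred, and it does not by itself threaten the primary conclusion. It merits a cheap improvement because selection before entry cannot be undone at analysis.

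**What to change.** Amend the Randomization section so that, for a twin pregnancy, the eligibility and consent status of both infants are recorded and locked in the randomisation website before the shared arm is displayed. In addition:

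- flag any co-twin who qualifies only after the arm is known, and keep that infant in the intention-to-treat primary analysis;
- pre-specify a sensitivity analysis that leaves flagged infants out of both arms, so that every remaining infant had its eligibility fixed before the arm was shown;
- tabulate non-enrolled co-twins by arm, with reasons.

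The cost is one extra website field and a short wait for the second twin's assessment within the 2-hour window. The same-arm rule and the sample size are unchanged. The lock does not restore concealment for a co-twin who qualifies later, but it makes such infants identifiable and their influence on the result measurable.
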